7.2 Primary Endpoints

7.2.1 Definition of Primary Endpoints

The TEAR rate during 24-week treatment period is the primary endpoint for this study. TEAR criteria is defined as either one of the following:

- 1) Subjects who are ADA negative at baseline and become positive at any timepoint post baseline.
- 2) Subjects who are ADA positive at baseline and demonstrate 4-fold increase in titer values at any timepoint post baseline visit.

Whether a subject sample is ADA positive or negative will be determined using screening and confirmatory assays in a tiered approach. Titer values will be further evaluated if a subject sample is confirmed ADA positive. If the subject is ADA positive at baseline, then the titer values of post baseline samples will be further evaluated to determine if there is a 4-fold increase versus baseline, indicating that the post-baseline sample(s) are treatment boosted ADA positives (see [Section 6.5.2.4](#) in protocol for detailed immunogenicity assessment information).

Although differences in TEAR rate is the primary endpoint for the study from a statistical perspective, given that immunogenicity is not a standard endpoint in clinical trials, this difference, even if significant, will not be assessed in isolation but will be part of totality of evidence including changes in HbA1c, FPG, insulin dose, neutralizing antibodies and injection site reactions to ensure that changes in TEAR rate, if any, are clinically correlated and meaningful.

7.2.2 Statistical Methodology for Primary Endpoints

The 90% confidence interval of treatment difference (MYL-1601D minus NovoLog®) in TEAR rate will be established using Wald confidence limit method. MYL-1601D TEAR rate is equivalent to that of NovoLog® during 24-week treatment period if 90% confidence interval of treatment difference in TEAR rate is within pre-specified margin defined in [Table 5](#). The pre-specified equivalent margin is dependent on the final rate of NovoLog® TEAR rate.

To minimize any bias due to missing data, multiple imputation will be used to fill in missing values for TEAR criteria (binary response and continuous titer values) prior to deriving the TEAR and subsequently estimating the treatment difference and 90% confidence interval.

The method of imputation for a subject will be dependent on the individual ADA result at baseline. For subjects with baseline ADA negative, post baseline binary response (positive or negative) will be imputed using logistic regression multiple imputation assuming missing not at random. For subjects with baseline positive, missing titer values (continuous values) will be imputed with same treatment group non-missing subjects using pattern mixture model with the complete-case missing values (CCMV) method ([Little 1993](#)).

In the case where there are sufficient number of retrieved dropouts, that is, if there are 6 retrieved dropout subjects in each treatment group, the missing values in that treatment group will be imputed by modelling the retrieved subgroup data. Retrieved dropout subjects are the subjects who discontinued assigned study treatment but still remain on the study and had their

efficacy and safety measurements captured at the planned visits. If less than 6 retrieved dropout subjects in each treatment group, all non-missing subjects within same treatment group will be used to impute missing data by multiple imputation.

If baseline value is missing, the missing baseline value will be imputed with single imputation based on binomial distribution using probability of no missing baseline values from same treatment group.

After imputation, the TEAR criteria will then be applied to each imputed dataset to obtain if a subject is TEAR positive or negative, and the treatment difference and 90% confidence interval will be estimated using Wald confidence limit method. The result will be combined over all imputations by SAS PROC MIANALYZE.

The primary analysis will be based on the ITT analysis set. In addition, all post-discontinuation and rescue data should be included in the analysis. Further analysis details analysis steps and example SAS codes will be provided in the SAP.

7.2.3 Primary Analysis for Primary Endpoints

Equivalence of TEAR rate will be established if 90% confidence interval of treatment difference (MYL-1601D minus NovoLog®) is within \pm margin indicated in Table 5. The pre-specified equivalence margin is based on the final NovoLog® TEAR rate. The primary analysis will be performed on the intent to treat (ITT) analysis set.

7.2.4 Secondary/Sensitivity Analyses for Primary Endpoints

- Same analysis model as the primary analysis, but without imputing missing values. This will be analyzed based on PP and ITT analysis set.
- In a derived TEAR dataset, for subjects in MYL-1601D treatment group with missing antibody values, TEAR responder will be replaced regardless if subject is TEAR responder or non-responder. The TEAR rate difference between two treatments and 90% confidence interval will be then estimated using Wald confidence limit method. This will be analyzed based on ITT.
- Tipping-point analysis using method proposed by [Liublinska and Rubin \(2014\)](#) will be performed. A graphic display (heating map) is used to indicate the tipping point analysis results with missing values as TEAR positive. The treatment differences are presented as values in the heat map. The graph will be displayed to show the sensitivity ranging from missing favour testing treatment to missing favour reference treatment.

For tipping-point analysis, number of subjects with missing data are either 1) subjects who miss completely post-baseline ADA data or 2) subjects who miss partially ADA data that cannot be determined if subject is TEAR positive or negative 3) subjects who miss at baseline. If a subject with partially ADA missing data already meet the TEAR criteria, the subject is not considered as subject with missing data.

- TEAR rate for each treatment and difference between treatments for missing data during treatment period will be summarized for all sensitivity analyses.
- In addition, incidence of TEAR rate at each scheduled visits: visitwise TEAR (vTEAR) will be summarized at each scheduled visit by using similar TEAR

definition: ADA negative at baseline become positive at specific visit (Treatment Induced TEAR), and ADA positive at baseline and become 4-fold increase in titer at specific visit (Treatment Boosted TEAR).

7.2.5 Missing Data

The only imputed data will be performed in the primary and sensitivity analyses as described above for TEAR rate associated with ADA and other secondary variables if deemed necessary. The detailed missing data imputation for other secondary variables will be included in SAP.

7.2.6 Sub-Group Analyses

Subgroup analyses of important factors, including but not limited to factors such as age group, gender, race, and ethnicity are planned for the key outcomes of TEAR rate. Wald confidence limit method for TEAR rate will be used for 90% confidence interval. Other exploratory subgroup analyses may be performed, as deemed appropriate.

7.3 Secondary Endpoints

The following efficacy measures (both actual and change values) will be summarized at baseline and scheduled visit. A mixed model repeated measures (MMRM)-effects model will be performed for continuous variables without imputing missing values. The MMRM model will include the fixed, categorical effect of treatment group assignment, visit, treatment group-by-visit interaction and the other fixed effect terms Investigator, basal insulin dose time, and baseline value as covariates. Contrasts of LS mean at each scheduled visit will be used to evaluate all pairwise treatment comparisons, and 95% confidence intervals for treatment differences in LS means will be computed for each visit.

- Change in HbA1c from baseline.
- Change in fasting plasma glucose from baseline.
- Change in prandial, basal insulin and total daily insulin dose per unit body weight (U/kg) from baseline.
- Change in 7-point SMBG profile from baseline.

All above analyses will be performed on ITT set.

A sensitivity analysis for HbA1c will be performed using multiple imputation to impute missing values with non-missing subjects within same treatment group using pattern mixture model with the complete-case missing values (CCMV) method ([Little 1993](#)). After imputation, treatment difference, 95% CI, and p-values will be generated using same MMRM model as above.

The following safety measures (both actual and change values) will be summarized at baseline and scheduled visit. Similar MMRM model as efficacy analysis will be conducted for hypoglycemia rate. For antibody continuous variables, the MMRM model will include the fixed, categorical effect of treatment group assignment, visit, treatment group-by-visit interaction and the other fixed effect terms Investigator and baseline value as covariates. Contrasts of LS mean at each scheduled visit will be used to evaluate all pairwise treatment

comparisons, and 95% confidence intervals for treatment differences in LS means will be computed for each visit. For categorical data analyses, Fisher's exact test or Chi-squared test will be used.

The following analyses will also be performed and will form part of the totality of evidence to compare clinical efficacy and safety of two treatment groups:

- Incidence of ADA response and positive cross-reactive ADA; and incidence of positive NABs.
- Analysis of potential impact of TEAR status on efficacy and safety parameters such as HbA1c, glucose control FPG, insulin dose, hypoglycemic rate, incidence of any injection site allergic reactions and hypersensitivity.
- Change in hypoglycemia rate (30 day adjusted) from baseline and incidence of hypoglycemic events at scheduled visits
- Incidence of TEAEs and SAEs
- Incidence of local allergic reactions, systemic allergic reactions and other adverse events
- Incidence of device-related safety assessment

To explore the potential ADA impact on subject's glucose control, the following analyses will be performed:

- The incidence of subjects with meeting all three following criteria will be summarized descriptively (for categorical measures) by treatment, by visit, and overall:
 - 1) Meet the vTEAR criteria
 - 2) Increases in HbA1c of over 0.2% from baseline
 - 3) Increase in total dose from baseline
- Scatter plots of maximum TEAR values with HbA1c, FPG and total daily insulin dose by treatment.

The total incidence of Device-related safety events will be summarized for each treatment group and would include device-related TEAEs and events related to device complaints or failures. For device-related TEAEs, two categories will be summarized for each treatment: needle-related TEAEs such as pain, bruise, and bleeding; and other device-related TEAEs, such as hyperglycemia or hypoglycemia. For device-related patient's complaints, incidence will be listed and summarized for each treatment.

All the above analyses will be performed on the safety set.

In addition, graphical visualization of relationship between adverse events and treatment duration will be provided.

The details of all safety analysis will be provided in the SAP.

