MYL-1601D (Mylan insulin aspart) is a rapid-acting human insulin analog. The primary activity of insulin aspart is the regulation of glucose metabolism, it binds to the insulin receptors on muscle and fat cells, and it leads to a decrease in blood glucose by facilitating the cellular uptake of glucose while simultaneously inhibiting the output of glucose from the liver. MYL-1601D is produced by recombinant DNA technology utilizing *Pichia pastoris* (yeast). The primary structure is identical to endogenous insulin, except for replacement of a single proline amino acid at position 28 in the C-terminal area of the insulin B-chain with an aspartic acid residue. This substitution weakens the natural tendency towards self-association between insulin monomers, thereby inhibiting aggregation into hexamers and accelerating absorption after sub-cutaneous injection.

The aim of this trial is to demonstrate the equivalence in the safety and efficacy profile between MYL-1601D and NovoLog® in patients with T1DM with primary focus on assessment of immunogenicity and its potential clinical impact on safety and efficacy.

In case of prandial insulins like aspart, PK-PD study using an euglycemic clamp is a very sensitive and robust tool to assess potential differences in efficacy between biosimilar products versus traditional endpoints like HbA1c. This approach of using PD parameters

from euglycemic clamp as a key surrogate efficacy measure has been acknowledged by both FDA and EMA. In this context, the current study in T1DM patients is primarily aimed at addressing residual uncertainty with specific focus on assessment of immunogenicity.

Systemic assessment of immunogenicity is a relatively new area and limited information and approaches are available for analyzing these data. Furthermore, the immunogenicity profile is highly dependent on the ADA assay format and thus data from one study cannot be easily extrapolated to another study especially with regards to incidence rates. The problem is further compounded by the fact that limited data is available from the innovator NovoLog® studies.

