8 STATISTICAL METHODS

8.1 General statistical conventions

All statistical procedures will be completed using SAS version 9.3 or higher.

Unless otherwise stated, all statistical testing will be two-sided and will be performed using a significance (alpha) level of 0.05. Two-sided 95 % confidence intervals (CI) will be provided when relevant. 4 digits after decimal point will be used for all p-values.

All quantitative endpoints will be summarized using an 8-number summary (n, mean, standard deviation, median, 25th quartile, 75th quartile, minimum and maximum values). Unless otherwise specified, minimum and maximum will be presented with same number of decimal places as reported/collected, one additional decimal place for mean, median, 25th quartile and 75th quartile, and two additional decimal places for standard deviation. All qualitative endpoints will be summarized by the number of subjects meeting the endpoint and the percentage of subjects out of the appropriate population. The denominator will be displayed when needed.

For retests, unscheduled visits and visit end of treatment, in general, for by-visit summaries, data recorded at the nominal visit will be presented. Unscheduled measurements will not be included in by-visit summaries but will contribute to the scheduled visit if scheduled visit value is missing or the Last Observation Carried Forward (LOCF) value in case primary sensitivity analysis. The same principle will be applied to the visit end of treatment data.

Early termination data will be entered under the Visit 14 (week 18), but for summary tables it will be mapped to the next available planned visit number after their last scheduled visit. For example, should a patient discontinue at Visit 9, the Early Termination visit will have their Fasting plasma glucose and their HbA1c assay taken. The fasting plasma glucose would then be summarized under Visit 10 and the HbA1c under Visit 11.

All subject data, including those derived, will be presented in individual subject data listings. Unless otherwise stated, unscheduled visit results will be included in date/time chronological order, within subject listings only. All listings will be sorted by investigational site, patient number, date/time and visit. The treatment group as well as patient's sex and age will be stated on each listing. Unless otherwise stated, data listings will be based on all subjects randomized.

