8.8 Safety analyses

Safety data from the run-in period will be summarized and listed on run-in analysis set.

Descriptive statistics will be provided for the following safety data. No inferential analysis of this safety data is planned. Any Vital signs, ECG, and Laboratory abnormalities of potential clinical concern will be described.

For the continuous safety measures, both actual and change values will be summarized at baseline and scheduled visit. Similar MMRM model as efficacy analysis will be conducted for hypoglycemia rate. For antibody continuous variables, the MMRM model will include the fixed, categorical effect of treatment group assignment, visit, treatment group-by-visit interaction and the other fixed effect terms investigator and baseline value as covariates. Contrasts of LS mean at each scheduled visit will be used to evaluate all pairwise treatment comparisons, and 95% confidence intervals for treatment differences in LS means will be computed for each visit. For categorical data analyses, Fisher's exact test or Chi-squared test will be used.

The following analyses will also be performed.

- Incidence of ADA response, incidence of positive cross-reactive ADA, and incidence of positive NABs
- Analysis of potential impact of TEAR status on efficacy and safety parameters such as HbA1c, FPG, insulin dose hypoglycemic rate, and incidence of any injection site allergic reactions and hypersensitivity
- Change in hypoglycemia rate (30 day adjusted) from baseline and incidence of hypoglycemic events at scheduled visits
- Incidence of TEAEs and SAEs
- Incidence of local allergic reactions, systemic allergic reactions and other adverse events
- Incidence of device-related safety assessment

To explore the potential ADA impact on subject's glucose control, the following analyses will be performed:

- The incidence of subjects with each of the three following criteria will be summarized descriptively (for categorical measures) by treatment:
 - 1) Meet TEAR criteria
 - 2) Increases in HbA1c of over 0.2% from baseline
 - 3) Increase in total dose from baseline
- Scatter plots of maximum tear values with HbA1c FPG and total daily insulin dose by treatment.

All the above analyses will be performed on the safety set.

In addition, graphical visualization of relationship between adverse events and treatment duration will be provided.

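### No confidence interval for the between-arm difference is pre-specified for the categorical safety and secondary immunogenicity incidences that support the equivalence conclusion

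*Protocol*

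**What the plan says.** Protocol 2.2 sets the goal: "The aim of this trial is to demonstrate the equivalence in the safety and efficacy profile" of the two products. The primary TEAR comparison follows from that goal, with a 90% CI for the difference set against a margin.

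Protocol 7.2.1 adds of the TEAR difference that "this difference, even if significant, will not be assessed in isolation but will be part of totality of evidence". The five items it names there are HbA1c, FPG, insulin dose, neutralizing antibodies and injection site reactions. The last two are incidences. Protocol 7.3 then lists further analyses that "will form part of the totality of evidence to compare clinical efficacy and safety of two treatment groups". They include the incidences of ADA, cross-reactive ADA, neutralizing antibodies, TEAEs, SAEs, and local and systemic allergic reactions. Hypersensitivity enters through the analysis of TEAR impact, and SAP 8.8.4 adds immune-mediated events.

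For continuous measures, Protocol 7.3 and SAP 8.7.3, 8.8 and 8.8.5 specify least-squares mean differences with 95% CIs. For categorical ones the method is: "For categorical data analyses, Fisher's exact test or Chi-squared test will be used". SAP 8.1 sets the default: "Unless otherwise stated, all statistical testing will be two-sided and will be performed using a significance (alpha) level of 0.05". It also says: "Two-sided 95 % confidence intervals (CI) will be provided when relevant".

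SAP 8.8 states "No inferential analysis of this safety data is planned", and in its next paragraph prescribes the Fisher or chi-squared tests and model contrasts with intervals.

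**The concern.** Fisher's exact test and the chi-squared test take no difference as the null hypothesis. In a superiority trial a non-significant result simply leaves the claim unproven. In an equivalence trial the same result points in the direction the sponsor hopes for, and it becomes more likely as events become rarer. What an equivalence argument needs is the range of differences the data still allow, which a p-value does not show.

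Injection site reactions, hypersensitivity and neutralizing antibodies are the consequences against which a TEAR difference is to be judged clinically meaningful or not. If these comparisons are summarised by a p-value, a result compatible with a sizeable excess on MYL-1601D could be taken as showing no clinical impact.

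**Working it through.** **Inputs.** 250 subjects per arm, 1:1, no attrition assumed (Protocol 4.1 and 7.1); two-sided alpha of 0.05 (SAP 8.1). The documents forecast no rate for any reaction, ADA or neutralizing-antibody endpoint, so every event rate below is an assumption.

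**The plan's own figure.** The only power statement is for TEAR. The margin formula with the quantiles in the SAP 10.2 code, (z0.95 + z0.90) × √(2p(1−p)/250), gives at p = 5%: (1.645 + 1.282) × √(2 × 0.05 × 0.95/250) = 2.926 × 0.0195 = 5.7 points. That matches Table 5, and the other eleven margins also reproduce to within rounding. No power figure exists for the categorical supporting comparisons, so there is none to reproduce.

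**Chance of missing a true doubling.** Take two independent Binomial(250, p) counts, enumerate all outcome pairs, and sum the probability that the test does not reach p ≤ 0.05. The chi-squared test is uncorrected.

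| Reference → test rate (assumed) | Missed, Fisher | Missed, chi-squared |
|---|---|---|
| 1% → 2% | 93% | 87% |
| 2% → 4% | 82% | 74% |
| 3% → 6% | 70% | 64% |
| 4% → 8% | 59% | 53% |
| 5% → 10% | 49% | 43% |
| 8% → 16% | 25% | 21% |
| 10% → 20% | 14% | 11% |
| 15% → 30% | 2% | 2% |

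**What an interval would show.** Suppose 10/250 events on MYL-1601D and 5/250 on NovoLog. Fisher p = 0.29 and chi-squared p = 0.19. The risk difference is 4.0% − 2.0% = +2.0 points. The Wilson limits are 2.19% to 7.21% for 10/250 and 0.86% to 4.60% for 5/250. The Newcombe 95% limits follow:
- lower: 2.0 − √((4.0 − 2.19)² + (4.60 − 2.0)²) = −1.2 points
- upper: 2.0 + √((7.21 − 4.0)² + (2.0 − 0.86)²) = +5.4 points

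So a non-significant result here leaves open an excess of up to 5.4 points over an observed reference rate of 2%.

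**Smaller denominators.** SAP 8.8.5 also presents injection site allergic reactions and hypersensitivity among TEAR-positive subjects. If 30% of each arm were TEAR positive (assumed; 0.30 × 250 = 75), Fisher would miss a doubling 98%, 87% and 68% of the time at base rates of 2%, 5% and 10%. At 50% TEAR positive (125 per arm) the figures are 93%, 77% and 46%.

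**The case against.** The strongest reply is that the plan never gives these p-values a decision role. Equivalence rests on the 90% CI for TEAR against the margin, and nothing lets a supporting p-value override it. A reader might infer that a non-significant result is meant to stand as reassurance, or could rescue a TEAR result that missed its margin. The documents do not say so: the totality wording is loose, but it contains no such rule. That part of the reply stands.

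A reader might also infer that the plan gives p-values and nothing else. That is too strong. SAP 8.1 requires counts and percentages for qualitative endpoints and allows 95% CIs where relevant. SAP 8.8.1 plans a graph of the most frequent adverse events sorted by risk difference. SAP 8.8.1 and 8.8.4 name no test of their own, and the table templates are in a separate document. With counts and denominators shown, a reader could compute an interval. But the graph covers only frequent events and specifies no interval, and the convention in SAP 8.1 names neither an endpoint nor a method. Neither is a commitment for neutralizing antibodies, ADA or uncommon reactions.

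The miss rates cannot be spread over every endpoint. They are high only for assumed rates of about 1% to 5%. ADA and neutralizing-antibody rates are not given, and Table 5 itself spans TEAR rates of 5% to 60%.

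Nor should the continuous endpoints be held up as well powered by contrast. On the arcsine effect-size scale, doublings from 1% and from 5% are effects of 0.08 and 0.19. A continuous difference of 0.08 to 0.19 SD with 250 per arm would be missed about 85% to 42% of the time. The continuous measures are better served because they come with intervals, whatever their power.

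**Conclusion.** The point holds as a gap in pre-specification. For the categorical incidences that "will form part of the totality of evidence", a difference test is the only between-arm inferential method named, and no interval for the difference is committed to, although the aim is equivalence and continuous measures do get intervals. A non-significant p-value could be read as similarity.

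The size depends on assumed rates. For an uncommon reaction (reference rate 1% to 5%, full 250 per arm) a true doubling would be missed about 93% to 49% of the time with Fisher and 87% to 43% with chi-squared. For common events the concern about missing a doubling largely disappears.

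The contradiction within SAP 8.8 needs no assumption: the section rules out inferential analysis of the safety data and then prescribes it. The primary TEAR analysis and its margin are not in question here. This is a worthwhile, inexpensive improvement to how supporting evidence is reported, and it does not affect the trial's main conclusion.

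**What to change.** In SAP 8.8 and 8.8.5, specify the risk difference (MYL-1601D minus NovoLog) with a two-sided 95% CI by the Newcombe or Miettinen-Nurminen method. Apply it to neutralizing antibodies, ADA, cross-reactive ADA, injection site and other local reactions, systemic allergic reactions, hypersensitivity and immune-mediated events, and overall TEAE and SAE incidence. State that these results are interpreted by the interval, that any p-value is descriptive, and that non-significance is not evidence of similarity. Reword the SAP 8.8 sentence on inferential analysis so that it agrees.

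Protocol 7.3 can be aligned if the protocol is amended for other reasons. Section 7 of the Protocol already lets the SAP modify its plans, with a protocol amendment required only for major changes to the primary endpoint or its analysis.

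The cost is SAP wording and a little more programming in tables already planned, with no new data or subjects. The intervals supply estimates and set no pass or fail threshold, and their limits will look less reassuring than a non-significant p-value.
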